Official Title:

Interactive and Adapted Physical Exercise for the Remote Management of
Chronic Low Back Pain

NCT number: Not Available

Unique Protocol ID: CLBPEO

Date: April 24th, 2023

Project Protocol

Experimental design

The study is an interventional proof-of-concept pilot study. Participants will be 45 people with CLBP aged 18 to 80 years who are able to consent, have no contraindication to physical activity, and can communicate, read, and understand French. Participants will be randomly divided into 3 groups: an interactive physical activity group, a video physical activity group, and a control group. Recruitment will be done from participant pools of multiple locations across Montréal and the province of Québec. The intervention will last 12 weeks and consist of 3 physical activity sessions per week for the intervention groups. The interactive group sessions will be interactive (and live) via Zoom and the video sessions will consist of be pre-recorded videos. The control group will be instructed to continue their lifestyle habits throughout the study.

Patient sample

For this study, participants will be adults between 18 years and 80 years of age, presenting with chronic low back pain (CLBP) for more than 6 months. Patients selected will need to respond to the criteria established by the Canadian minimum dataset for CLBP (Lacasse et al., 2017). Other inclusion criteria will include having an internet connection and access to a computer with webcam or tablet and be able to follow a physical activity program, which will be assessed with the Questionnaire sur l'Aptitude à l'Activité Physique (QAAP questionnaire). Individuals with a history of psychiatric or neurological illness will be excluded. Participants will not be eligible for the study if they have neuropathic signs (radiating pain that spreads to the knee and leg (http://www.physio-pedia.com/Red_Flags_in_Spinal_Conditions).

Participants will be recruited from: 1) the Quebec Pain Research Network (QPRN) participant pool (>3000 CLBP patients), 2) the *Centre de Recherche de l'Institut Universitaire de Gériatrie de Montréal* (CRIUGM) participant pool (>1000 seniors), 3) the Quebec Chronic Pain Association (QCPA) low back pain participant pool, 4) former participants of the laboratory's research projects who have agreed to be recontacted, 5) the pool of people with low back pain attending the *Institut universitaire sur la réadaptation en déficience physique de Montréal* and the *Clinique d'adaptation à la douleur chronique du Centre de réadaptation Lucie-Bruneau*. Participants will be randomly assigned to one of 3 groups.

Dependent variables

In addition to the inclusion criteria, assessments will be performed at weeks 0 (pre) and 12 (post-intervention) following a videoconference or telephone format and using lime-survey©. This mode of evaluation is done to make long-term implantation feasible and flexible for any geographical location, and also in case of restrictions, including due to weather or the current pandemic.

These assessments will measure:

- 1) CLBP intensity using the national Institutes of Health minimum (NIH) dataset.

 The primary outcome will be pain intensity perceived on average for the previous 7 days, reported in an 11-point numerical rating scale from 0 (no pain) to 10 (maximum imaginable pain)
- 2) CLBP outcomes from the NIH minimum dataset, including: 5 dimensions of pain history, 4 dimensions of medical interventions for CLBP, 4 dimensions of pain interference, 4 dimensions of physical function, 4 dimensions of depressive symptoms, 4 dimensions of sleep, 2 items on absenteeism due to

- CLBP, Kinesiophobia, Pain catastrophizing, 2 items on substance abuse, 1 item on smoking and the patient's height and weight to calculate their bodymass index
- 3) Physical health (functional capacity: SPPB, unipodal balance, Timed Up and Go (TUG); physical performance: lower extremity power (10 repetition chair test, 30sec chair test), gait speed (4 minutes fastest possible gait). Patients will rate pain intensity before and after each of these tests in an 11-point numerical rating scale from 0 (no pain) to 10 (maximum imaginable pain)
- 4) Pain intensity before and after each session attended. Participants will be asked to rate in an 11-point numerical rating scale from 0 (no pain) to 10 (maximum imaginable pain), the low back pain intensity perceived while standing, lying down and walking, before and after each training session
- 5) Finally, the adherence (number of sessions; minimum threshold of 75% to be considered complete, and 66% or 4/6 sessions in the last two weeks) to both remote interventions will be assessed.

Independent variables

A computer application (random-number generator) will be used to generate a randomization sequence and thus assign each patient to one of the three groups. The intervention will last 12 weeks. Physical activity sessions for both intervention groups will take place 3 times per week (Monday, Wednesday, Friday) providing a total of approximately 180 min/week. The intensity of each session is categorized by levels 1, 2 or 3 and the allocation to this level is decided according to a decision tree taking into account the mobility profile of each participant (balance and cardiomuscular health).

Interactive physical activity group (IPA, n=15): The sessions will be provided to groups of about 10 people and will be interactive via the Zoom conference medium (the link will be sent to them by email). They will last 1h30 min and will consist of 60 min of physical activity, preceded and followed by 15 optional minutes of virtual social interaction with the kinesiologist and the other members of the group. This training mode will allow the kinesiologist to correct the participants in real time during the sessions while creating a sense of belonging. Finally, if the participants are unable to attend the group session, a video of the course given will be available for them to follow afterwards via a website.

Virtual physical activity group (VPA, n=15): The sessions will be conducted individually without interaction via pre-recorded videos. The videos are identical to those of courses given by the kinesiologist to the IPA group. Participants will be able to contact the kinesiologist by phone or email to ask questions about the sessions.

The control group (CTL, n=15) will be instructed to continue their lifestyle habits throughout the study. The interactive physical training program will be offered after the 12-week wait. Participants in the control group will follow the training regimen of the IPA group.

Procedures

The study will have a total estimated duration of two years, during which each patient will participate in 36 sessions divided into 3 weekly sessions for 12 weeks. The research protocol consists of several stages. Initially, participants are contacted via telephone and administered a questionnaire. If they are deemed eligible for the study, they proceed to the next stage, otherwise, their participation is terminated at this stage. Participants who are eligible for the study are then given access to LimeSurvey, an online

survey platform to provide questionnaire data. Eligible participants undergo an online physical evaluation via the Zoom platform, which also serves to confirm their recruitment. Only participants who successfully meet the inclusion criteria after completing the physical evaluation proceed to the next stage.

At this point, participants are randomly allocated to either be placed on a waiting list, given access to receive videos (group VPA), or assigned to participate in the interactive Zoom classes (group IPA). Those on the waiting list are contacted for a final online evaluation at a later date. Participants in the VPA group are given access to a video platform and contacted for a final evaluation at a later date. Participants assigned to the IPA group are managed by Neuromotrix, a team of kinesiologists specialized in adapted physical activity. Neuromotrix provides them with three Zoom meetings per week and a reminder email on Sundays prior to every week. These participants are also contacted for an online final evaluation at a later date. All participants undergo a final physical assessment on the date of the final evaluation, after which they complete a final questionnaire on LimeSurvey.

Statistical analysis plan

Homoscedasticity will be verified using the Levene test. Descriptive statistics will be employed to define the sample characteristics. The main outcome variable (average pain intensity due to CLBP) will be compared between groups (IPA, VPA and CTL) over time at the primary endpoint (baseline and week 12) using a mixed analysis of variance (ANOVA). Other secondary outcomes will be similarly examined by using mixed ANOVAs to compare groups and effects. Age, gender and baseline pain intensity will be used as covariates. For exploratory purposes, changes in pain intensity (delta = post – pre)

before and after each session will be averaged across sessions and the means compared within and between groups to evaluate acute changes in pain intensity (positive or negative) immediately after the exercise session. In addition, the mean rate of attendance to sessions in the IPA and VPA groups will be compared by means of a non-paired t-test to interpret adherence data.

References

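### Continuous secondary outcomes are compared as change scores; a week-12 ANCOVA on each outcome's own week-0 value would usually be more precise

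*Combined protocol and SAP*

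**What the plan says.** The Statistical analysis plan sets out the method for the primary outcome, which is "compared between groups (IPA, VPA and CTL) over time at the primary endpoint (baseline and week 12") by mixed ANOVA. Secondary outcomes follow the same route: "Other secondary outcomes will be similarly examined by using mixed ANOVAs to compare groups and effects". The next sentence gives one covariate list: "Age, gender and baseline pain intensity will be used as covariates".

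Under Dependent variables, "assessments will be performed at weeks 0 (pre) and 12 (post-intervention"), so every outcome in those assessments has its own week-0 value. The continuous or score-type outcomes include "4 dimensions of pain interference, 4 dimensions of physical function" in item 2, with kinesiophobia and catastrophizing, and "functional capacity: SPPB, unipodal balance, Timed Up and Go (TUG") in item 3, with the chair tests and gait speed.

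Under Independent variables each arm has 15 participants (for example "The control group (CTL, n=15")). Under Experimental design, "The study is an interventional proof-of-concept pilot study".

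The documents do not say which term of the mixed ANOVA is tested or whether covariates interact with time. They give no SD or pre-post correlation and plan no confidence intervals. Per-session pain change and attendance have their own analyses and are outside this point.

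**The concern.** The covariate list suits the primary outcome, because baseline pain is that outcome's own starting value. For Timed Up and Go, SPPB or catastrophizing, baseline pain is a different variable, and the outcome's own starting value is not on the list. It is used only as the first of two repeated measurements.

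With two time points, a group-by-time contrast is a comparison of mean change. Subtracting the week-0 value assumes that one unit higher at week 0 predicts one unit higher at week 12. Regression to the mean usually makes that slope less than 1, and ANCOVA estimates it from the data.

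What is at stake is precision. With 15 per arm the intervals for arm differences are wide on either method, and some of that width could be avoided using data the trial already collects.

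**Working it through.** **Inputs from the documents:** three arms of 15 (total 45); weeks 0 and 12; covariates age, gender and baseline pain. There is no precision figure in the plan to reproduce.

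**Assumed inputs:** pre-post correlation rho from 0.3 to 0.9; ratio k of week-12 SD to week-0 SD (1 unless stated); correlation r of baseline pain with the outcome's week-0 value from 0 to 0.5; two-sided 95% intervals; normal data; no missing values; age and gender unrelated to the outcome.

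**Step 1, large-sample formula, pain unrelated (r = 0).** In units of the week-0 variance, the residual variance is 1 + k² − 2·rho·k for the change score and k²(1 − rho²) for ANCOVA. With k = 1, the ratio of interval widths is sqrt[2(1 − rho)/(1 − rho²)] = sqrt[2/(1 + rho)].

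- rho 0.3: sqrt(2/1.3) = 1.240
- rho 0.5: sqrt(2/1.5) = 1.155
- rho 0.7: sqrt(2/1.7) = 1.085

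**Step 2, baseline pain already in both models.** If pain relates to week 12 only through the own week-0 value, the ratio is sqrt{[2(1 − rho) − (1 − rho)²r²]/(1 − rho²)}. At r = 0.5:

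- rho 0.3: sqrt[(1.4 − 0.1225)/0.91] = 1.185
- rho 0.5: sqrt[(1 − 0.0625)/0.75] = 1.118
- rho 0.7: sqrt[(0.6 − 0.0225)/0.51] = 1.064

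**Step 3, trial size.** Change on arm, age, gender and pain leaves 45 − 6 = 39 residual df. The week-12 value on the same terms plus the own week-0 value leaves 45 − 7 = 38. The first model corresponds to a mixed ANOVA whose covariates interact with time. Ratio of mean 95% half-widths, change score over ANCOVA, in 6,000 simulated trials per setting with equal SDs:

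| rho | r = 0 | r = 0.3 | r = 0.5 |
|---|---|---|---|
| 0.3 | 1.225 | 1.203 | 1.166 |
| 0.5 | 1.139 | 1.126 | 1.103 |
| 0.7 | 1.068 | 1.061 | 1.050 |
| 0.8 | 1.040 | 1.036 | 1.027 |
| 0.9 | 1.011 | 1.009 | 1.006 |

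These lie slightly below the formula values because the extra covariate has a small cost at this sample size. At r = 0.3 the half-widths are 0.89 against 0.74, 0.75 against 0.67, and 0.59 against 0.55 SD at rho 0.3, 0.5 and 0.7.

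**Step 4, sensitivity to the assumptions** (extra width of the change-score interval):

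- Pain also linked directly to week 12 (correlation 0 to 0.5, equal SDs, rho 0.3-0.7): −1% to +35%.
- k = 1.2: 10-13%, 4-6% and 0% at rho 0.3, 0.5 and 0.7, and −1% at 0.8.
- k = 1.43: 5-7%, 1% and −1% at rho 0.3, 0.5 and 0.7. With r = 0 the large-sample gain is zero when k = 1/rho, and 1/0.7 = 1.43.
- k = 0.8: 30-39%, 24-30% and 19-25% at rho 0.3, 0.5 and 0.7.
- Covariates not interacting with time, so that the contrast is an unadjusted change score (42 df), equal SDs, pain acting only through week 0: 18%, 9-10%, 3%, 0% and −3% at rho 0.3, 0.5, 0.7, 0.8 and 0.9. With a direct pain link this reaches about +44% at rho 0.7.

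**Step 5, worst case for the proposal.** Against the covariate-adjusted change score, the lowest ratio over k = 1, 1.2 and 1.43 and rho 0.3-0.9 was 0.986, so ANCOVA was at most 1/0.986 − 1 = 1.4% wider. Against the change score whose covariates do not interact with time, ANCOVA was about 5% wider at k = 1.43 and rho 0.7.

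**The case against.** The strongest reply is that the planned analysis is valid, concerns only secondary outcomes of a 45-person pilot, and that choosing ANCOVA instead is a matter of method preference. Validity is not in dispute, and this is why the point ranks low. It is still more than taste: the gain can be calculated, the data are already collected, and the cost is small.

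Four stronger inferences are tempting, and the documents do not support them:

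- *That baseline is ignored or the comparison is biased.* The week-0 value is in the model as a repeated measure, and under randomisation the change comparison is unbiased.
- *That the plan commits to intervals of a given width.* It plans none. The figures describe intervals implied by the model on its natural reading.
- *That about 5-23% follows from a pre-post correlation of 0.3-0.7 and equal SDs alone.* It also needs baseline pain to act on week 12 only through the own week-0 value, and covariates that interact with time. Without the pain assumption the range is about -1% to +35%.
- *That adding the own week-0 value to the mixed ANOVA's covariate list is enough.* Entered only as a between-subject main effect, it leaves the group-by-time contrast unchanged. The arm comparison itself has to be respecified.

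It is also fair to object that a week-12 model does not describe change within arms. That is met by keeping the mixed ANOVA for description. The objection that correlations may be 0.8-0.9, where little is gained, stands: nothing in the documents excludes it. The documents do not describe score distributions either, so the normal-data figures are approximate.

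**Conclusion.** The point holds as a modest, inexpensive gain in precision for continuous secondary outcomes. Under the assumptions in the working (15 per arm, equal SDs, pain correlated 0 to 0.5 with the own week-0 value and acting only through it, covariates interacting with time), the change-score intervals are about 17-23%, 10-14% and 5-7% wider than ANCOVA at correlations of 0.3, 0.5 and 0.7, and 1-4% wider at 0.8-0.9. None of these inputs except arm size comes from the documents. The gain grows if the week-12 SD is smaller than the week-0 SD, and can vanish or turn slightly negative if it is larger. Worth considering; medium confidence in the size.

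**What to change.** In the Statistical analysis plan, for the arm comparison of each continuous secondary outcome, regress the week-12 value on arm, that outcome's own week-0 value, age, gender and baseline pain. The own baseline is added to the listed covariates and does not replace baseline pain. Report arm differences with 95% CIs. The mixed ANOVA may be kept to describe change over time within arms. The rewording also settles which term is tested.

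Cost: SAP wording and one residual degree of freedom (38 instead of 39 with 45 participants), with no new data, visits or participants. With high correlation or a larger week-12 SD, intervals may be about 1% wider than the covariate-adjusted change score, or up to about 5% wider than a change score whose covariates do not interact with time.

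### Baseline pain is both a response and a covariate in the primary mixed ANOVA, with no deciding term named; a stated week-12 ANCOVA would settle the model cheaply

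*Combined protocol and SAP*

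**What the plan says.** The primary outcome is defined under Dependent variables: "The primary outcome will be pain intensity perceived on average for the previous 7 days", on a 0 to 10 numerical rating scale (NRS). The same section gives two assessment times: "assessments will be performed at weeks 0 (pre) and 12 (post-intervention").

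The Statistical analysis plan compares this outcome between the three groups "over time at the primary endpoint (baseline and week 12) using a mixed analysis of variance (ANOVA"). The next sentence turns to other outcomes: "Other secondary outcomes will be similarly examined by using mixed ANOVAs to compare groups and effects". The covariate sentence follows without qualification: "Age, gender and baseline pain intensity will be used as covariates".

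The plan does not name the term that decides the primary comparison. It does not say whether the covariates enter as main effects or crossed with time, or how baseline pain can be a covariate when it is also one of the two response values. No ANCOVA is mentioned. Experimental design describes the study's status: "The study is an interventional proof-of-concept pilot study".

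**The concern.** With only two time points, half of the response data are the baseline values, and the same values are listed as a covariate. What that does depends on how the model is set up. A covariate that is constant within a person cannot alter a within-person contrast unless it is crossed with time. An analyst who adds the three covariates in the usual menu-driven way may therefore believe the primary test is adjusted when the group-by-time line is not.

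This is the only planned analysis of the primary outcome, in 45 people. Two analysts following the text could report different F tests and different interval widths from the same data. One common software route also gives a test that rejects too often.

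**Working it through.** **Inputs.** From the documents: 45 participants, 15 per arm (Experimental design; Independent variables), two time points and three covariates. The documents give no alpha, SD, effect size, power or baseline to week-12 correlation, so there is no stated calculation to reproduce. Assumed: 5% test, complete data, age and gender unrelated to pain, correlation ρ from 0.3 to 0.85, and k = week-12 SD / baseline SD of 0.8, 1.0 or 1.2.

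**1. What each set-up tests.** Let Y0 and Y12 be pain at baseline and week 12, D = Y12 − Y0, and x the covariates (including Y0).

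- *Main effects only.* The term in x is the same at both times and cancels in D. The group-by-time test is the one-way ANOVA of D, with 45 − 3 = 42 residual df.
- *Crossed with time.* D is regressed on arm and x. As Y12 = D + Y0, replacing D by Y12 only shifts the coefficient of Y0 by 1. The residuals and the arm F are those of the week-12 ANCOVA, with 45 − 3 − 3 = 39 residual df.
- *Between-group line under main effects.* It tests (Y0 + Y12)/2 on arm and x. Given Y0, this is Y12/2 plus a constant, so its F also equals the week-12 ANCOVA F.

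On simulated data sets all three identities held to rounding error. One data set generated with ρ = 0.5 shows the possible divergence: F(2,42) = 1.248, p = 0.298 with main effects, against F(2,39) = 2.854, p = 0.070 with crossing or ANCOVA. It is an illustration, not a typical difference.

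**2. Main-effect entry in a random-intercept model** (k = 1, variances in units of σ²). The fitted slope on Y0 averages 1 (baseline rows) and ρ (week-12 rows), giving (1+ρ)/2. The remainders are +(1−ρ)/2·Y0 at baseline and −(1−ρ)/2·Y0 plus error at week 12. They are negatively correlated, so the intercept variance is estimated at zero.

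- Variance the model then assigns to a change: (1−ρ)(3+ρ)/2.
- True variance of a change: 2(1−ρ).
- Ratio: (3+ρ)/4 = 0.825, 0.875, 0.925 at ρ = 0.3, 0.5, 0.7.

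The estimates are unchanged but the SE is too small. In the data set above it fell from 0.566 to 0.536. With the intercept variance set to zero, simulated type I error (6,000 trials per setting) was 8.5, 7.6 and 6.6% at ρ = 0.3, 0.5 and 0.7, with simulation error of up to about 0.4 points. The classical change-score and ANCOVA tests held 4.8 to 5.2%.

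**3. Precision.** Per-person variances, in units of the baseline variance:

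- change score: 1 + k² − 2kρ
- ANCOVA: k²(1 − ρ²)

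For k = 1 the ratio is (1−ρ²)/[2(1−ρ)] = (1+ρ)/2. Its square root is the CI ratio before the cost of estimating three covariate slopes. Simulation includes that cost, which is about 4% (for example 0.839/0.806 = 1.04).

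| k | CI ratio, ANCOVA to change | ρ = 0.3 | 0.5 | 0.7 | 0.85 |
|---|---|---|---|---|---|
| 1.0 | formula | 0.806 | 0.866 | 0.922 | 0.962 |
| 1.0 | simulated | 0.839 | 0.900 | 0.959 | 1.001 |
| 1.2 | formula | 0.873 | 0.933 | 0.983 | 0.999 |
| 1.2 | simulated | 0.91 | 0.97 | 1.02 | 1.04 |
| 0.8 | formula | 0.709 | 0.756 | 0.792 | 0.796 |
| 0.8 | simulated | 0.74 | 0.79 | 0.83 | 0.83 |

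Worked cell, k = 1.2 and ρ = 0.7: ANCOVA 1.44 × 0.51 = 0.734; change 1 + 1.44 − 1.68 = 0.76; √(0.734/0.76) = 0.983; × 1.04 = 1.02.

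In scale units, with k = 1, ρ = 0.5 and an assumed SD of 2 points, the mean CI half-width for a pair of arms is 1.46 NRS points (change) against 1.32 (ANCOVA). With a 0.6 SD benefit in both exercise arms and k = 1, power of the three-arm test is 26/35/55/86% (change) against 36/43/59/86% (ANCOVA) at ρ = 0.3/0.5/0.7/0.85.

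**The case against.** The strongest reply has four parts.

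- *The covariates are probably meant for the primary outcome.* The secondary outcomes are to be analysed in the same way as the primary one, and the covariate sentence carries no restriction. It most plausibly covers all the mixed ANOVAs. This stands. A reader might infer that the primary test is unadjusted on most readings of the plan, but the text does not support such a count. Limiting the covariates to secondary outcomes is the least natural reading, and the plan never says that group-by-time decides. If the between-group line decides, main-effect entry already gives the ANCOVA test. How the covariates enter, and which line is read, remain open.
- *If the covariates are crossed with time, ANCOVA changes nothing.* Also true. The fix then only records what was intended.
- *The gain is not assured.* It depends on a correlation and an SD ratio that the documents do not give. With equal SDs, break-even is at a correlation of about 0.85; with week-12 SD 1.2 times baseline, it falls between 0.5 and 0.7. A reader might infer that ANCOVA loses precision only above 0.85, but that holds only under equal SDs.
- *It is a pilot.* With no power target or decision rule, differences in power carry little weight. This limits the stakes. It does not remove the value of a narrower interval or of a primary test that is fixed in advance.

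**Conclusion.** The concern holds as one of specification and precision. The primary model has baseline pain on both sides, and the plan leaves open both the deciding term and the form of adjustment. Depending on that choice, the group-by-time test is the unadjusted change-score test or the week-12 ANCOVA.

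A reader might go further and call the planned analysis invalid. The documents do not support that: the classical mixed ANOVA holds its 5% level with either form of covariate entry. Nor can one say that every implementation is safe, because main-effect entry in a random-intercept fit gave type I error of about 6-8% at correlation 0.7 to 0.3.

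Under the stated assumptions with equal SDs, ANCOVA narrows the interval by about 16, 10, 4 and 0% at correlation 0.3, 0.5, 0.7 and 0.85. With week-12 SD 1.2 times baseline, it is about 9% and 3% narrower at 0.3 and 0.5, and 2-4% wider at 0.7 to 0.85. With 0.8 times, it is 17-26% narrower. Nothing here shows that the sample size is wrong. The change is a cheap improvement worth making.

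**What to change.** Replace the primary-analysis wording with an ANCOVA: week-12 average pain as the outcome, randomised arm as the factor, and baseline pain, age and gender as covariates. Name the arm effect (2 and 39 df with complete data) as the primary test. Report adjusted week-12 differences between arms in NRS points with 95% CIs. Say whether the covariates also apply to the secondary outcomes.

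The arm effect remains an omnibus test, so pairwise contrasts and multiplicity still need their own statement.

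Cost: one or two sentences, three residual df (42 to 39), and slightly wider intervals if the correlation is high or pain is more variable at week 12 than at baseline. No new data, participants or visits are needed.

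### Averaging signed session pain changes hides flare-ups that are offset by relief, and the protocol and SAP describe no recording of falls, injuries or flares during remote exercise

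*Combined protocol and SAP*

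**What the plan says.** Under Dependent variables, item 4 is "Pain intensity before and after each session attended". On a 0-10 scale, participants rate "the low back pain intensity perceived while standing, lying down and walking, before and after each training session".

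The Statistical analysis plan uses these ratings as follows: "For exploratory purposes, changes in pain intensity (delta = post – pre") are to be "averaged across sessions and the means compared within and between groups to evaluate acute changes in pain intensity (positive or negative"). It plans no count, proportion, threshold or maximum for sessions or participants with increased pain, and does not say how the three posture ratings become one change score.

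Exposure is set out in Procedures ("each patient will participate in 36 sessions divided into 3 weekly sessions for 12 weeks") and in Independent variables, with 15 people in each exercise arm. For the video arm (VPA): "The sessions will be conducted individually without interaction via pre-recorded videos". The control arm has no study sessions during the 12 weeks. Experimental design gives the population: "Participants will be 45 people with CLBP aged 18 to 80 years".

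The list of assessments ends with adherence. Nothing in the supplied protocol and SAP defines, collects or tabulates adverse events, falls, injuries or flare-ups.

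**The concern.** The session analysis says it wants to see acute change in both directions, but the chosen summary collapses the two directions into their balance. A participant whose pain often rises sharply and often falls can have the same mean as one whose pain never moves. An arm in which a few people clearly worsen and most improve slightly can have the same mean as an arm in which nobody changes.

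This matters because no other measure is linked to the training sessions themselves. Live correction by the kinesiologist is what the protocol presents as distinctive about the interactive arm (IPA), so how sessions are tolerated with and without it is a natural question for a pilot, although the documents do not state it as an objective. As written, the trial could report similar mean acute changes in IPA and VPA without being able to say whether flares were equally frequent. Because events are not recorded, it could not put any bound on the risk of a fall or injury.

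**Working it through.** The documents give no power, effect size or SD for the session ratings, so there is no design figure to reproduce. The stated counts agree: 3 × 15 = 45 participants and 3 × 12 = 36 sessions. Flare sizes, flare frequencies and SDs below are assumptions.

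**1. Cancellation within a person.** Let a share q of sessions rise by f points and the rest fall by 1. The mean is qf − (1 − q), which is 0 when q = 1/(1 + f).

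| Rise f | Share q giving mean 0 | Sessions of 36 |
|---|---|---|
| +2 | 33% | 12 |
| +3 | 25% | 9 |
| +4 | 20% | 7.2 |

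Check for +3: (9 × 3 − 27 × 1)/36 = 0, with 9/36 = 25% of sessions up by at least 2 points.

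**2. Cancellation between people.** Twelve participants at −1 and three at +4: (−12 + 12)/15 = 0.

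**3. With session noise.** Simulating the +3/−1 pattern for 15 participants and 36 sessions, with noise of SD 1 (3,000 trials), about 21% of sessions rise by at least 2 points. A one-sample t-test on the participant means finds worsening in about 2.6% of trials, against a nominal 2.5% in that direction.

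**4. What the mean can show.** Eighteen sessions at +3 and 18 at −1 give (54 − 18)/36 = +1.0, a net worsening. Power for a net 1-point change (two-sided 5%, noncentral t), by assumed SD of participant means:

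| SD | Within one arm of 15 | IPA v VPA, 15 each |
|---|---|---|
| 1.0 | 95% | 75% |
| 1.5 | 67% | 42% |
| 2.0 | 44% | 26% |

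**5. Equal means, different flare rates.** Assume a mean change of −0.2 in both arms and within-person SDs of 1.5 and 2.5.
- Continuous scale: 1 − Φ(2.2/1.5) = 7.1% (2.6 of 36 sessions) and 1 − Φ(2.2/2.5) = 18.9% (6.8 of 36), a ratio of about 2.7.
- Whole-number changes, where 2 or more begins at 1.5: 1 − Φ(1.7/1.5) = 12.9% (4.6 of 36) and 1 − Φ(1.7/2.5) = 24.8% (8.9 of 36), a ratio of about 1.9.

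**6. What event recording would give.** Planned exercise sessions are 2 × 15 × 36 = 1,080, or 810 at 75% attendance. With zero events in n people, the one-sided 95% upper bound is 1 − 0.05^(1/n), which is 18.1% for n = 15 and 9.5% for n = 30. The chance of at least one event among 30 is 1 − 0.95^30 = 79% at a true risk of 5%, and 1 − 0.90^30 = 96% at 10%.

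**The case against.** Three stronger readings are tempting, and the documents do not support them.

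- A reader might infer that the planned mean cannot show worsening at all. It can: a net rise makes it positive, the SAP allows for both directions, and step 4 shows moderate to good power within an arm unless the SD is large.
- A reader might infer that this is the trial's only measure of harm. It is not. The 7-day average pain (the primary outcome), pain around the physical tests, pain interference and physical function could all show worsening. However, they are assessed at weeks 0 and 12, so a flare that has resolved in between can be missed, and none of them records a fall or injury.
- A reader might infer that one arm could have several times more flares behind equal means. Step 5 gives about 1.9 to 2.7 times, and only by assuming unequal SDs for which the documents give no basis.

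Other points stand in the plan's favour. The analysis is labelled exploratory and is never called a safety record. Entry is screened with an activity-readiness questionnaire and a physical evaluation. Exercise level follows a decision tree that considers balance, and VPA participants can phone or email the kinesiologist. IPA members who miss a class can follow a video, so unsupervised sessions are not confined to VPA. All this bears on the level of risk, but none of it records what happens. The averaging problem can also be repaired after the data are in, because the individual ratings are collected. Unrecorded events cannot be recovered in that way.

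**Conclusion.** The point holds in limited form. The planned summary shows net acute change, but not the frequency or severity of flares that are offset by relief. That is arithmetic and needs no assumption about SD. How much would be hidden in this trial is unknown: the 25% and 21% figures are illustrations with assumed flare sizes and noise.

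Separately, the supplied text describes no recording of falls, injuries or flares during remote exercise. Consent pages were not available, so this finding covers the protocol and SAP text only.

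Two limits also affect the session data. Only attended sessions are rated, so a session missed because of a flare contributes nothing. With no control sessions during the 12 weeks, the between-group session comparison in that period can only be IPA versus VPA. The change is worth making because it serves the plan's own aim at little cost. It does not affect the primary analysis.

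**What to change.** 1. In the Statistical analysis plan, keep the mean delta and add, for IPA versus VPA, each participant's share of attended sessions with a worsening of at least a prespecified size, the share with an improvement of the same size, and the largest single-session rise. State how the standing, lying and walking ratings are combined. This needs a few lines of text and no new data, but the cut-off must be fixed in advance.
2. Add one yes/no item on fall, injury or pain flare to the post-session rating, compared for IPA versus VPA only. Add the same item to the week-12 survey in all three arms, and report both with exact confidence intervals.
3. Make any three-arm comparison from the week-12 item alone. Exercisers would otherwise be asked up to 36 more times than controls, and the unequal ascertainment would bias the table. The week-12 item also captures events that stopped attendance, in those who complete the survey.

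The costs are slightly longer forms, 12-week recall for the survey item, and wide intervals: zero events in an arm of 15 still leaves an upper bound of 18%. Sample size and treatment are unchanged.
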